8.2.4 Analysis of Exploratory Endpoints

Bone biomarkers that are correlated with objective response will be identified using a Wilcoxon rank sum test comparing biomarker levels in those with and without objective response to treatment. The expression of PD-L1 and other immunologic biomarkers will be compared in biopsies before therapy, on-treatment, and at progression using a Wilcoxon signed-rank test on each pair of observations. As appropriate, expression levels will be dichotomized to meaningfully present versus not present.

8.2.5 Sample Size

The proposed study is a single-arm, phase I/II study of pembrolizumab in combination with cabozantinib in subjects with metastatic RCC. We will use a Simon two-stage design for the phase II portion this study based on the primary endpoint of objective response rate. The planned enrollment for this study is approximately 25-55 total subjects, to account for screen failures, in order to achieve 6-9 evaluable subjects in Phase I dose escalation and 20-38 evaluable subjects in Phase II dose expansion. Subjects from the Phase I part of the study who are treated at the RP2D may be included in the efficacy assessments in Stage I of the Phase II part of the study.

Phase I:

Any subject who does not complete the DLT assessment window for any reason other than a DLT will be considered non-evaluable for dose-escalation decisions and MTD and RP2D assessment and will be replaced by an additional subject at that same dose level.

Table 12 describes the probability of not observing any DLTs in 3 subjects, and the probability of observing fewer than two DLTs in 6 subjects for different underlying DLT rates.

| Underlying DLT Rate | Probability of Observing No DLTs in 3 Subjects | Probability of Observing Fewer Than Two DLTs in 6 Subjects |
|---------------------|---|---|
| 0.10 | 0.73 | 0.89 |
| 0.20 | 0.51 | 0.66 |
| 0.33 | 0.30 | 0.36 |
| 0.40 | 0.22 | 0.23 |
| 0.50 | 0.13 | 0.11 |
| 0.60 | 0.06 | 0.04 |

Table 12: Probability of Observing DLTs for Different Underlying DLT Rates

For a given adverse event with a true rate of 10%, 5%, or 1%, the probability of observing at least one such adverse event in a given cohort of 6 subjects is 47%, 26.5%, and 5.8%, respectively.

Phase II:

The Simon's two-stage design will be implemented to test the null hypothesis that $ORR \le 0.20$ versus the alternative that $ORR \ge 0.50$. After the enrollment of 20 evaluable patients in the first stage, the trial will be terminated if 2 or fewer respond. If the trial goes on to the second stage, a total of 38 patients will be studied. If the total number responding is greater than 12, the treatment is considered effective.

This two-stage design has an expected sample size of 34.29 and a probability of early termination of 0.206. If the drug is actually not effective, there is a 0.029 (satisfied the 0.05 type I error rate constraint) probability of concluding that it is. If the drug is actually effective, there is a 0.017 probability of concluding that it is not, which corresponding to a 98% power (satisfied the 90% power constraint).

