8.2.3 Analysis of Anti-Tumor Activity

Descriptive statistics will be used to summarize all demographic and analytic data. Continuous data will be summarized using means, standard deviation, range, etc. Categorical data will be summarized using frequency tables.

Tumor response analyses will be based on definitions of responses according to both RECIST v1.1 and immune-related response criteria (irRECIST).

Objective response is defined as a complete or partial response, as determined by investigator assessment using RECIST and irRECIST. Subjects with missing or no response assessments will be classified as non-responders. For the primary objective, a one-sided exact binomial test will be used to assess whether the ORR is significantly greater than 20% in subjects taking a combination of pembrolizumab and cabozantinib.

Clinical benefit rate (CR + PR +SD) and duration will also be recorded.

Among subjects with an objective response, duration of response will be defined as the time from first occurrence of a documented objective response until the time of documented disease progression or death from any cause during the study, whichever occurs first. For all other subjects, duration of objective response will be censored at the day of the last tumor assessment.

Progression-free survival (PFS) will be defined as the time from study treatment initiation (Cycle 1, Day 1) to the first occurrence of documented disease progression or death from any cause during the study, whichever occurs first. For subjects who do not have documented progressive disease or death during the study, PFS will be censored at the day of the last tumor assessment.

Overall survival (OS) will be defined as the time from study treatment initiation (Cycle 1, Day 1) to death from any cause. For subjects who do not have documented death during or after the study, OS will be censored at the day of known survival status.

In subjects with bone metastases, time to progression of bone metastases or skeletal related event (SRE, defined as pathologic fracture, spinal cord compression, and radiation to bone or surgery to bone related to cancer) will also be recorded from Cycle 1 Day 1 to the time of progression or SRE.

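### The stage I futility bound in 8.2.5 (2 or fewer of 20) stops a regimen at the 20% null only 20.6% of the time; a bound of 3 doubles that at almost no cost in power

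*Combined protocol and SAP*

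**What the plan says.** Section 8.2.5 tests a null ORR of 0.20 or less against an alternative of 0.50 or more. The stage I decision comes "After the enrollment of 20 evaluable patients in the first stage": "the trial will be terminated if 2 or fewer respond". Then: "If the trial goes on to the second stage, a total of 38 patients will be studied", and "If the total number responding is greater than 12, the treatment is considered effective". The section reports "an expected sample size of 34.29 and a probability of early termination of 0.206", a type I error of 0.029 against a limit of 0.05, and 98% power against a required 90%. It gives no reason for a bound of 2, and it does not describe the design as optimal or minimax.

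Section 2.1.7 gives a different rule for the same stages: stop only if fewer than 2 of 20 respond, and declare the treatment effective at 12 or more of 38.

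**The concern.** A futility look is there to spare subjects the second stage when the regimen is no better than the null. At a true ORR of 0.20, the 8.2.5 rule goes on to enrol the remaining 18 subjects about four times in five. It does so even at 3 of 20, an observed rate of 15%, below the rate the trial is meant to exceed. Power is 98% where 90% was required, so there is room for a bound that stops more often. At stake is the number of subjects treated in a second stage that has almost no chance of success.

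**Working it through.** **Inputs, all from 8.2.5:** n1 = 20, n = 38 (so n2 = 18), stop if X1 ≤ r1 with r1 = 2, success if the total exceeds 12, p0 = 0.20, p1 = 0.50.

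**Formulas (exact binomial):**
- Early termination: PET = P(X1 ≤ r1), X1 ~ Bin(20, p).
- Expected N = 20 + 18 × (1 − PET).
- P(declare effective) = Σ over x1 > r1 of P(X1 = x1) × P(X2 ≥ 13 − x1), X2 ~ Bin(18, p).

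**Step 1, the plan's figures.** At p = 0.20, P(0), P(1) and P(2) are 0.0115, 0.0576 and 0.1369, so PET = 0.206. Expected N = 20 + 18 × (1 − 0.2061) = 34.29. Type I error is 0.0288. At p = 0.50, power is 0.9832, so the type II error is 0.017. All agree with the document.

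**Step 2, what continuing at 3/20 is worth.** From 3 responses, success needs 13 − 3 = 10 or more of 18, or 56%. The probability of that is 0.09% at ORR 0.20, 13% at 0.40 and 41% at 0.50.

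**Step 3, move only the stage I bound.**

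| At p0 = 0.20 | stop ≤2 | stop ≤3 | stop ≤4 |
|---|---|---|---|
| Early termination | 0.206 | 0.411 | 0.630 |
| Expected N | 34.29 | 30.59 | 26.67 |
| Mean saving out of 38 | 3.7 | 7.4 | 11.3 |
| Type I error | 0.0288 | 0.0286 | 0.0277 |

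| True ORR | Early stop ≤2 / ≤3 / ≤4 | P(declare effective) ≤2 / ≤3 / ≤4 |
|---|---|---|
| 0.30 | 3.5% / 10.7% / 23.8% | 0.341 / 0.340 / 0.332 |
| 0.35 | 1.2% / 4.4% / 11.8% | 0.601 / 0.599 / 0.588 |
| 0.40 | 0.4% / 1.6% / 5.1% | 0.813 / 0.812 / 0.803 |
| 0.50 | 0.02% / 0.13% / 0.59% | 0.9832 / 0.9827 / 0.9800 |

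ORRs of 0.30 to 0.40 are assumptions; the plan names only 0.20 and 0.50.

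**Step 4, direct check of the cost of moving from 2 to 3.** The only successes lost are those with exactly 3 in stage I and at least 10 of 18 after it:
- ORR 0.50: 0.00109 × 0.407 = 0.00044, or 0.04 points.
- ORR 0.40: 0.01235 × 0.135 = 0.0017, or 0.17 points.
- ORR 0.35: 0.0323 × 0.0597 = 0.0019, or 0.19 points, the largest loss among the rates checked from 0.30 to 0.50.

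**Step 5, the 2.1.7 rule.** Stopping at 1 or fewer, with success at 12 or more, gives early termination 0.069, expected N 36.75, alpha 0.0623 and power 0.993. Alpha is above the 0.05 limit stated in 8.2.5.

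**The case against.** The strongest reply is that this is a choice, not a defect. The plan discloses the 0.206, meets both its constraints and claims no optimality. That stands.

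The 20% null is also not an inactive regimen. Sections 4.1 and 4.1.1.2 cite response rates of 25% for nivolumab and 21% for cabozantinib as single agents, and the trial summary calls cabozantinib standard therapy. Against a clearly poorer regimen the present rule works well, stopping 68% of the time at ORR 0.10. A reader might infer that the look protects almost nobody. The documents do not support that: even at 0.20 it saves 3.7 subjects on average.

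A lenient look may also suit slow or incomplete ascertainment. Imaging is after every 3 cycles (7.1.2.5), missing assessments count as non-response (8.2.3), and the population mixes immunotherapy-naive and pretreated subjects (4.2.1). The plan does not give these as its reason, but the point has weight. Suppose, as an assumption, that at a true ORR of 0.50 only 80% or 60% of eventual responses are recorded at the look, so that the count behaves like 0.40 or 0.30. A bound of 3 would then stop 1.6% or 10.7% of the time, against 0.4% or 3.5% with a bound of 2.

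This argument counts mainly against a bound of 4, which stops at an observed rate equal to the null. It raises early stopping from 3.5% to 23.8% at ORR 0.30 and from 0.4% to 5.1% at 0.40. Each early stop also cuts the data for the secondary endpoints in 3.2. A bound of 3 stops only at 15% or less, below the null.

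**Conclusion.** The 8.2.5 rule is valid and correctly reported, but weak as a futility look. Changing the bound from 2 to 3 raises early termination at the null from 0.206 to 0.411 and saves a further 3.7 subjects on average (34.29 − 30.59). It costs under 0.2 points of power at each ORR checked from 0.30 to 0.50. These figures assume that n = 38 and success above 12 are kept, and that responses are fully recorded at the look.

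Two stronger readings are tempting. The first is that the design is wrong because it is not one of Simon's standard designs for 0.20 against 0.50 with alpha 0.05 and 90% power. The optimal design is 2/10 then 7/22 (expected N 13.9) and the minimax is 2/12 then 7/21 (expected N 16.0). The plan claims to be neither, so this is not an error. The second is that a bound of 4 is plainly better because it triples early stopping for 0.3 points of power. That loss holds only at ORR 0.50; it is 1.1 points at 0.40, with the extra early stopping described above.

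Whether the change can still be made is unknown. Section 5.2.1.3.2 provides for subjects already past 35 cycles at the October 2020 version, and the appendix pages carry a June 2021 date. The look may therefore have taken place, but the documents do not say.

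**What to change.** If the stage I look has not been made, set the 8.2.5 bound at 3 or fewer of 20, keep n = 38 and success above 12, and restate early termination 0.411, expected N 30.6, alpha 0.029 and power 98%. If the sponsor prefers 4 or fewer (0.630, 26.7, 0.028, 98.0%), 8.2.5 should say that the extra early stopping at ORR 0.30 to 0.40 and the loss of secondary-endpoint data were weighed. If 2 is kept, give the reason.

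In every case reconcile 2.1.7 with 8.2.5. Both its futility and its success bounds differ, so this means editing two sections, not changing a single number.

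If the look has been made, state which bound was applied and do not change it afterwards.

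The cost is a short amendment with no added subjects. With a bound of 3, early stopping rises from 3.5% to 10.7% at ORR 0.30 and from 0.4% to 1.6% at 0.40.

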9.0 LABELING, PACKAGING, STORAGE AND RETURN OF CLINICAL SUPPLIES

9.1 Investigational Product- Pembrolizumab

The investigator shall take responsibility for and shall take all steps to maintain appropriate records and ensure appropriate supply, storage, handling, distribution and usage of investigational product in accordance with the protocol, Investigator's Brochure, and any applicable laws and regulations.

Clinical Supplies will be provided by Merck as summarized in Table 13.

Table 13: Product Descriptions

| Product Name & Potency | Dosage Form |
|---------------------------|----------------------------------|
| Pembrolizumab 50 mg | Lyophilized Powder for Injection |
| Pembrolizumab 100 mg/ 4mL | Solution for Injection |

9.2 Cabozantinib

Cabozantinib (Cabometyx®) will be prescribed and obtained commercially as tablets through a specialty pharmacy, per standard of care.

Refer to the package insert for additional information.

9.3 Packaging and Labeling Information

Clinical supplies will be affixed with a clinical label in accordance with regulatory requirements.

9.4 Clinical Supplies Disclosure

This trial is open-label; therefore, the subject, the trial site personnel, the Sponsor and/or designee are not blinded to treatment. Drug identity (name, strength) is included in the label text; random code/disclosure envelopes or lists are not provided.

9.5 Storage and Handling Requirements

Clinical supplies must be stored in a secure, limited-access location under the storage conditions specified on the label.

Receipt and dispensing of trial medication must be recorded by an authorized person at the trial site.

Clinical supplies may not be used for any purpose other than that stated in the protocol.

9.6 Returns and Reconciliation

The investigator is responsible for keeping accurate records of the clinical supplies received from Merck or designee, the amount dispensed to and returned by the subjects and the amount remaining at the conclusion of the trial.

Upon completion or termination of the study, all unused and/or partially used investigational product will be destroyed at the site per institutional policy. It is the Investigator's responsibility to arrange for disposal of all empty containers, provided that procedures for proper disposal have been established according to applicable federal, state, local and institutional guidelines and procedures, and provided that appropriate records of disposal are kept.

10.0 ADMINISTRATIVE AND REGULATORY DETAILS

10.1 Confidentiality

To maintain subject privacy, study drug accountability records, study reports, and communications will identify the subject by initials where permitted and/or by the assigned subject number. The subject's confidentiality will be maintained and will not be made publicly available to the extent permitted by the applicable laws and regulations.

Qualified representatives from the relevant regulatory agencies, the drug manufacturer (Merck), or its agents may inspect the subject/study records. Subject data obtained during the study may be presented in scientific publications, but at no time will subject names be used.

10.2 Conflict of Interest Policy and Compliance with Financial Disclosure Requirements

Independence of this study from any actual or perceived influence, such as by the pharmaceutical industry, is critical. Any actual conflict of interest of persons who have a role in the design, conduct, analysis, publication, or any aspect of this trial will be disclosed and managed.by the University of Colorado Denver's (UCD) Office of Regulatory Compliance Conflict of Interest and Commitment Management (COIC) program. Persons with a perceived conflict of interest will have such conflicts managed in a way that is appropriate to their participation in the trial. Conflict of Interest management plans are project-specific and are reviewed at least annually. UCD has integrated the institutional conflict of interest management program with its existing program.

Financial Disclosure requirements are outlined in the US Food and Drug Administration Regulations, Financial Disclosure by Clinical Investigators (21 CFR Part 54). All investigators participating in this trial will also be required to complete a Financial Disclosure Form (FDF) to provide his/her financial interests in and/or arrangements with the Sponsor-Investigator, and/or a manufacturer of the investigational agent(s) being studied in this clinical trial. The submission of an FDF must be a complete and accurate certification and disclosure of financial interests held by the investigators.

10.3 Compliance with Law, Audit and Debarment

The Sponsor-Investigator will ensure that this study is conducted in full conformity with regulations for the Protection of Human Subjects of Research codified in 45 CFR Part 46, 21 CFR Part 50, 21 CFR Part 56. International Conference on Harmonisation (ICH) Guidance on Good Clinical Practice ([GCP] CPMP/ICH/135/95) may also be followed to the extent it has been adopted by and is in accordance with FDA regulations.

Clinical monitoring of all study site locations will be allowed periodically, in accordance with the CMP, to assess data quality and study integrity. On site, they will review study records and directly compare them with the original source documents, discuss the conduct of the study with the investigator, and verify that the facilities remain acceptable.

In addition, the study may be evaluated by auditors designated by the Sponsor-Investigator and by government inspectors who must be allowed access to CRFs, source documents, and all other study files. Sponsor-Investigator audit reports will be kept confidential.

| Project Title: | Creative Arts Therapy (CAT) in the Center for Cancer and Blood Disorders |
|-------------------------|---|
| Principal Investigator: | [name], MSN, CPNP |
| Co-Investigators: | [name], CPNP |

Version Date: 5/10/2019

I. Hypotheses and Specific Aims

The purpose of the study is to evaluate the effectiveness of Creative Arts Therapy (CAT) on pediatric patients undergoing chemotherapy in the Infusion Center at Children's Hospital Colorado Center for Cancer and Blood Disorders. Findings from a previous pilot study support the hypothesis that CAT may improve quality of life (QOL), resiliency, physical posture, and emotional response to pain of pediatric oncology patients undergoing chemotherapy.

Specific aims include:

- a. Does CAT improve the child's reported QOL?
- b. Is the child's resiliency enhanced by CAT?
- c. Does CAT influence the physical posture of the child?
- d. Does CAT impact the child's emotional response to pain?
- e. Are patients, families, and staff satisfied with the CAT program?

II. Background and Significance

Although survival rates of children with cancer are improving, their QOL is known to be poorer than their healthy peers. As survival rates of pediatric cancer now approach 85%, the need for quality psychosocial care including creative arts has increased (Askins & Moore, 2008). Oncology patients are known to have significant morbidity during treatment as a result of the surgery, radiation and chemotherapy, but little is published on the day to day effects of treatment on the quality of life of pediatric oncology patients (Banks, 2008). Tremolada et al looked at parental perception of QOL in newly diagnosed children with leukemia and found that increasing the knowledge of QOL may improve communication and psychosocial care during initial treatment for leukemia (2010). In addition, quality of life among adolescents with cancer may be worse during treatment than for those not currently on therapy (Ward-Smith et al., 2007). Another study has shown that interventions to promote happiness may be a good predictor of QOL in adolescent survivors (Bitsko et al., 2008).

It has been acknowledged that even the act of coming to the clinic weekly for chemotherapy infusions impacts on the patient's life. In addition, vincristine, a commonly used chemotherapy, is also well-known to cause significant morbidity (leg pain, numbness, tingling, and constipation) requiring dose-limiting regimes. Steroids are another common medication with toxicities affecting QOL. Toxicities of steroids include weakness, sleep and mood disturbance, and pain with dose reduction (Sanford et al., 2008; Hinds et al., 2007).

Resilience is a subset of QOL that has been studied in pediatric chronic illness including cancer (Haase et al., 2004). Resilience has been defined as a characteristic that moderates stress and the ability to cope with change or misfortune (Wagnild & Young, 1993). Resilient individuals have positive outcomes in spite of adversity (Rew & Horner, 2003). Therefore nurses who understand resilience can promote those characteristics during times of illness or stress (Ahern et al., 2006). There is a paucity of literature directly studying resilience in pediatric oncology patients and further work is warranted.

Emotional response to pain is another subset of QOL that has been measured in this population. It is well known that pediatric oncology patients experience pain (Lervat, 2009). Experts recommend rigorous research using established measures to evaluate childrens' response to pain (McGrath et al., 2008). The Faces scale has been studied with children as young as 5 years to evaluate their emotional response to pain compared with their parents' perceptions (Breau et al., 2001). Pilot data on emotional response on the Faces scale has been shown to improve after group CAT (Madden et al., 2010).

Physical functioning and muscle strength are aspects of QOL that have been shown to be worse than healthy peers in children with cancer (Hartman et al., 2008). This aspect may also be affected by the central venous access lines placed in almost all pediatric cancer patients. Long-term central venous access is critical in pediatric cancer patients and the evolution of these devices has improved QOL in terms of pain and distress of venipuncture (Spagrud, 2008). The literature is rich with discussion of complications and risk of infection, but little is published about the effects on body image and QOL (Albanese, 1993; Nam, 2010). Anecdotally, patients have improved body awareness and posture (less kyphosis) after CAT. In addition, it has been postulated that increased kyphosis may correspond with psychosocial factors including anxiety, depression, and insecurity. Body awareness is a type of physical functioning that may be measured by kyphosis. Measuring posture with an inclinometer has been shown to be reliable, but further work is needed to establish validity (Lewis & Valentine, 2010). Piloting this tool may establish a way to physically measure an individual's sense of self by the way that he or she stands.

The use of complementary and alternative medicine (CAM) is one intervention that has been shown to improve QOL in this population. Current trends show increasing popularity of the use of CAM in even among children with cancer. Martel et al (2005) looked at prevalence of use of CAM in children. In their survey, almost 50% of the children used at least one type of CAM. Specifically to cancer, in 2009, Post-White et al used a survey of 281 patients to show that CAM was used in 59% of pediatric cancer patients versus 36% of general pediatric patients. The authors confirmed that children with cancer and other chronic illnesses use more CAM therapies than children seen in primary care clinics. Roth et al (2009) examined pediatric oncologists' perceptions of CAM and found that although they place importance in CAM, they lack time and knowledge to ask about patients' use of CAM. These authors recommend CAM research in pediatric oncology on modalities that could improve QOL.

CAT is a subset of CAM that may improve QOL. CAT is a broad term encompassing the modalities of dance/movement, music, art. Bringing creativity into health care is a current trend in oncology nursing and throughout the medical professions (Garland et al., 2007; Lane, 2006; Petterson, 2001; Strickland, 2008). There is a growing body of literature establishing the use

of CAT, but the studies use non-standardized tools, small sample sizes, adult populations, and non-rigorous designs. Much of the work on CAT in cancer patients studies adult populations using qualitative measures (Forzoni et al, 2010; Jones et al., 2009; Visser, et al, 2008; Bar-Sela, et al., 2007; Nainis et al., 2006). Other work looked at the family caregivers of patients with cancer and showed significantly reduced stress, anxiety, and increased positive emotions after a creative arts intervention (Walsh et al., 2004). Randomized controlled studies are in the literature and have shown improvement in QOL, but only for the population of women with breast cancer (Oster et al, 2006; Monti et al, 2006; Svensk et al, 2009; Thyme et al, 2009). Music was shown to decrease heart rate in children with leukemia, but the therapeutic aspects were not studied (Kemper et al., 2008). The literature is rich with other examples of types of music, art, movement therapies that may improve QOL in adult and pediatric oncology patients, but there are few rigorous studies to document the importance of CAT during the cancer treatment (Sencer et al, 2007; Dibell-Hope, 2000; O'Callaghan et al, 2007; Robb et al, 2003; Barrera, 2002; Hilliard, 2006).

Therefore, a pilot study of CAT on the QOL of pediatric brain tumor patients used a mixedmodel approach with a randomized, controlled phase comparing CAT to a control. Pre- and post- measurements using the PedsQL showed statistically significant improvement on Parent report of child's hurt (problems with having a lot of pain), p=0.03 and Parent report of child's nausea (becoming nauseated while thinking about medical treatment), p=0.0061. The second non-randomized phase pre- and post- tested any child in group session of CAT. The subjects showed improved mood with statistical significance on the Faces Scale (p < 0.01), and patients were more excited (p < 0.05), happier (p < 0.02), and less nervous (p < 0.02) on the Emotional Responses Checklist (Madden et al, 2010).

Rationale

The pilot study was limited by the small sample size; therefore we propose a study with a larger sample size and broader inclusion criteria. We would also like to explore outcomes of resilience and body awareness measured by physical posture based on our observations during the pilot study.

Significance

Nurses have been shown to provide valuable information on QOL for this population (Klaassen et al, 2010). In addition, the pediatric oncology nurse is in a key position to incorporate the art and science of nursing to improve psychosocial treatment outcomes (Cantrell, 2007). Therefore this nursing research study will provide valuable insight to contribute to the body of knowledge of CAM for pediatric oncology patients. The use of CAM for pediatric oncology patients may improve QOL, resiliency, emotional response, and body awareness.

III. Preliminary Studies/Progress Report

See above regarding the previous pilot study. Small sample size limited the statistical significance.

IV. Research Methods

A. Outcome Measure(s)

1. Peds QL—Cancer module

The PedsQL 4.0 Cancer Module is evolved from the PedsQL 4.0 Generic Core Scale (Varni, 1998). The system employs a Parent-Proxy Report for ages 2-18 years and a companion Child Self-Report for children aged five years and older. Validity and reliability testing for both the Core Scale and Cancer Module has been extensive.

Reliability, assessed by internal consistency, yielded coefficient alphas ranging from .80-.90 across total and individual scales and are, thus, appropriate for the group comparisons planned in this study. The Cancer Module is a 27-item instrument that assesses eight subscales (Pain and hurt, nausea, procedural anxiety, treatment anxiety, worry, cognitive problems, perceived physical appearance, and communication). It is easily completed by parents in less than 10 minutes and reverse-scored and linearly-transformed in five minutes or less. Validity for both the Core Scale and the Cancer Module was established by expert panel review; similarly, construct validity for both measures was performed by comparing the responses of children with cancer across both measures to a group of healthy matched controls. In all cases, the Peds QL 4.0 Cancer Module was able to distinguish the responses of children with cancer from those of healthy children at a statistically significant level.

The instruments have been successfully employed in several small studies of children with cancer (Bhat, 2005; Meeske et al, 2004). The PedsQL has been shown to be the most responsive to change when compared with other measures of QOL used with children undergoing chemotherapy (Banks et al, 2008; Klaassen et al, 2010).

2. The Resilience Scale (RS)

The RS-14 is a 14-item scale using a 7-point rating (1-7). The construct of resilience is measured by two factors: personal competence and acceptance of self and life. Wagnild and Young have completed psychometric testing that established internal consistency reliability and concurrent validity (Wagnild & Young, 1993). Many studies have validated that the scale may be used with samples of any age or ethnic background (Ahern et al, 2006), but it is written at a 6th grade level. The authors who developed the tool are currently using it in adolescents (personal communication, 5/25/10). Given that it is expected that half the population of this study will be teenagers, this tool will be used with subjects ages 12 and over to obtain initial data on CAT's effect on resilience.

3. Faces Scale

The Faces Scale has been used for evaluating emotional responses to pain on children 3-17 years old. It is a one page form with nine faces in order of happy to upset. Numerical values are given to each face as determined by childrens' perspectives for an affective value by asking 200 children to directly scale the feelings depicted by the faces. Consistent rating was measured by children over 5 years regardless of age, gender, or health status (McGrath, 1990). The scale is a facial affective scale and has been integrated as a routine measure for management of acute, recurrent, and chronic pain (McGrath, 1990; McGrath et al., 1996). For children less than 3 years old, parents will be asked to complete the Faces Scale. Although this scale has been used for emotional response to pain, it is felt to be an appropriate measure for the emotional response to the discomfort and anxiety in the infusion room.

4. Postural Measurement

Thoracic kyphosis will be measured using two gravity dependent inclinometers (Isomed Inc.). Spinal processes will be determined by palpation by a registered nurse or pediatric nurse practitioner. The feet of the inclinometers will be placed over the spinal processes thought to be at T1, T2 and T12, L1. The measurements will be taken in relaxed standing and measured 3 times in succession. Clinical assessment of the thoracic kyphosis angle is considered essential in postural examination, but can be time

consuming when measured radiographically (Lewis, 2010). Lewis and Valentine studied intra-rater reliability in subjects with and without symptoms and found measurements of less than 1.7 degrees should be considered measurement error. The test-re-test reliability established excellent intra-rater reliability. Although validity of this measure is less studied, the measurement is thought to provide guidance of how much change of the kyphoscoliosis angle is a real consequence of intervention over time (Lewis, 2010).

5. Patient/Family Surveys

A brief ten minute written survey will be administered to subjects to ascertain level of satisfaction with the program.

B. Description of Population to be Enrolled: Study Design and Research Methods

1. Population

The Center for Cancer and Blood Disorders (CCBD) at Children's Hospital Colorado sees approximately 240 new Oncology patients each year. Approximately 45% of these patients receive vincristine, a chemotherapy agent that is known to affect physical functioning. In addition, about 25% of these patients receive steroids, another medication known to affect physical functioning and quality of life. About half of the new patients each year are anticipated to fit the inclusion criteria. Therefore, we expect approximately 100 eligible subjects per year, with a 50% attrition rate, for a total sample size of 100 subjects over a two year period.

Enrollment for this study was reached in 2019. At this time, an additional 10 patients will be allowed to enroll on study to help supplement the data.

2. Eligibility Criteria

Inclusion

- Center for Cancer and Blood Disorders (CCBD) patient with Oncology or Neuro-oncology diagnosis
- No more than 2 previous sessions of CAT as an outpatient in the CCBD
- English speaking
- Receiving outpatient chemotherapy, biotherapy, or transfusions in the infusion center approximately weekly for at least 3 months.
- Ages 3 to 18 years

Exclusion

- Hematology or other patients in the infusion center
- Patients who have previously received more than 2 sessions of CAT in the infusion center
- Non-English speaking patients

3. Study Design

A repeated measures design will be used with each patient serving as his/her own control.

Any Oncology patient in the CCBD who has not previously received more than two sessions of CAT in the outpatient unit and who will be receiving approximately weekly infusions of at least one hour in the infusion center will be identified by a research assistant. The study will be explained to the patient/family and informed consent will

be obtained by the principal investigator or the research assistant. A demographic form will be completed including the information of diagnosis, age, treatment, educational level of parents, zip code, prior experience with art, music, movement.

The intervention will consist of approximately weekly CAT in the infusion center during cancer therapy. The interventionist is a Master's prepared, licensed dance/movement therapist who is experienced in music and art therapies as well. The CAT includes dance/movement such as playing with a parachute, simple yoga breathing and postures, and work with physioballs. The music includes singing, listening to music, and playing instruments. The art consists of drawing, finger painting, working with clay. The CAT may occur in individual sessions in private infusion rooms, or in groups in the middle of the infusion center. The CAT is not only a distraction, but also a therapeutic process addressing the stressors of cancer and its treatment. The "dose" of CAT will be recorded (number and type of sessions) and will be factored into the analysis.

The subjects and/or parents will be tested with all instruments before the intervention, and approximately every 30 days for no less than 3 months and a maximum participation of 6 months. Treatment time points will be at least 30 days apart. Because some subjects are not scheduled to come into the clinic every 30 days for SOC appointments, they are unable to complete 3 sessions of CAT in a 3 month time period. For those subjects who are scheduled to come into clinic every 1-2 months for SOC appointments, study participation may take up to 6 months. This 6 month time period would allow for the completion of 4 different time points of CAT.

The testing will take place in an exam room after vital signs have been completed upon intake to the clinic. The trained research assistant, trained RN, or PI will administer the questionnaires. The PedsQL includes a subject report (ages 5 and over) and a parent report. The Resilience Scale is a self-report and will be used for ages 12 and over. The Faces Scale will use parent report for ages less than 5 and self-report for ages 5 and over. In order to confirm consistency, the posture measure will be completed by the PI (nurse practitioner) or registered nurse on the study after training with the manual included with the inclinometer tool.

Off Study Criteria

1. Subject discontinues CAT

2. Unable to complete 4 time points in 6 months

C. Description, Risks and Justification of Procedures and Data Collection Tools

The anticipated risks include psychological distress incurred by completing the outcome measure questionnaires as well as the therapeutic process. This risk will be minimized by the presence of the Master's prepared, experienced dance/movement therapist. The patients' social workers through the clinic will be available during the intervention as well.

D. Potential Scientific Problems

Based on the pilot data, the anticipated scientific problem is slow accrual due to unforeseen events during the traumatic time of a new diagnosis in pediatric oncology. We are unable to randomize because CAT is standard of care for any patient in the infusion center and therefore we feel it is unethical to deny CAT to a control arm. Therefore, we will compare the subjects to themselves over time to look at longitudinal changes of CAT.

E. Data Analysis Plan

The primary outcome is Peds QL at approximately 3 months; secondary outcomes will be the Resilience Scale, Faces Scale, and postural measurement at approximately 3 months. A repeated measures analysis of variance will be used to analyze the primary and secondary outcomes. We will also use the repeated measures analysis of covariance with the addition of covariates, depending on their statistical significance, such as gender, age, cancer diagnosis, and previous exposure to arts/music/dance. All of the analysis will be adjusted for baseline measures.

